PRECIS

Being overweight or obese can cause insulin resistance (IR), which is defined as reduced responsiveness to insulin by the cells of various tissues or organs. IR at midlife increases the risk of developing Alzheimer's disease (AD). We recently discovered novel biomarkers of brain IR (altered Tyr and Ser phosphorylated forms of insulin receptor substrate 1; IRS-1) in plasma exosomes enriched for neuronal origin. Moreover, IR is associated with AD biomarkers including deficits in resting state brain activity and cognitive performance. Calorie restriction is defined as consuming fewer calories than what is considered normal without a lack of nutrients. A certain type of calorie restriction, in which one consumes 500-600 calories a day for two consecutive days, followed by non-restricted eating for 5 days (5-2 CR), has been shown to lower peripheral insulin resistance effectively. Effects of CR and lowering peripheral IR on brain IR and cognition are unknown. The goal of this exploratory pilot study is to provide proof-of-concept that 5-2 CR at midlife can reverse brain IR, lower peripheral IR, improve cognitive performance, and increase brain activation at rest and during tasks. Specifically, we will study the effects of 8 weeks of 5-2 CR versus a control dietary intervention on brain and peripheral IR, memory and executive function, resting state default mode network activity, brain metabolism, and AD biomarkers. Forty overweight to obese women and men (between 55 and 70 years of age) will be randomized 1:1 into 5-2 CR and control groups. In the 5-2 CR group, participants will be offered "healthy living" dietary counseling at baseline, which they will be instructed to implement for five days/week. For each of the other two consecutive days/week, they will consume two shakes (Boost®, CWI Medical), providing a total of 480 Kcal/day. In the control group, participants will be offered "healthy living" dietary counseling at baseline, which they will be asked to implement for every day of the week. Participants will undergo screening including a history and physical examination, calculation of Body Mass Index (BMI, which must be ≥ 27) and a blood draw for insulin and glucose to determine whether they have insulin resistance. If participants meet eligibility criteria, they will continue with a baseline visit involving anthropometric measures, questionnaires, tests of cognitive function, brain MRI, blood draws for plasma and peripheral blood mononuclear cells, and lumbar puncture for cerebrospinal fluid biomarkers of AD. After 8 weeks, we will collect the same measures. To assess and reinforce compliance with their respective diet, participants will come into the clinic every 2 weeks to discuss compliance, measure their body weight and perform blood draws for measurement of ketones to objectively confirm energy restriction for the 5-2 CR group. We will also contact participants every week to further ensure compliance. To assess the effects of the diets on physical activity, participants will be asked to wear an accelerometer for 96 hours before and after they are on the diet.

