The study is comprised of: an initial telephone pre-screening to describe the study and inclusion/exclusion criteria to potential participants; a "Screening Visit"; randomization into one of two groups; a "Baseline Visit"; the "Outcome Visit" after 8 weeks. During the 8-week period for the 5-2 CR or control groups, participants will return every two weeks for "Compliance Visits", to assess and reinforce dietary compliance in keeping with previous protocols.^{39,40,94} The Outcome Visit will take place at the conclusion of the 8-week phase. Specifically for the 5-2 CR group, the Outcome Visit will be timed during the second of the two CR days. In total, there will be 6 outpatient visits to the NIA Clinical Unit: Screening Visit, Baseline Visit, Week 2 Compliance Visit, Week 4 Compliance Visit, Week 6 Compliance Visit, and the Week 8 Outcome Visit. There will be an additional follow-up phone call or electronic mail within 3 days of completing the Week 8 Visit to assess any problems related to their final visit. Accelerometry will be implemented on two occasions for 96 hours each time: once between the screening and baseline visits and again after the Week 8 Outcome Visit. Throughout the study, additional safety visits may take place for any clinically significant. Participants will be involved in the study for approximately 8 – 11 weeks (allowing for an up to 3 week gap between Screening and Baseline Visits). Study participation will end with completion of accelerometry after the Week 8 Outcome Visit.

It is anticipated that participants in this study will occasionally miss or fail to complete an assessment or procedure, such as a completion of a rating scale or a blood draw. Omissions such as these will be considered expected events and not protocol deviations provided they are infrequent and do not include data needed to assess safety or the primary study outcome. Cumulative proportions of these missed events in the study population will be presented to the IRB annually. In addition, the rate of omissions will be monitored by the Investigators. If an individual misses more than 15% of the required assessments/procedures or if more than 15% of the participants miss completion of the same assessment or procedure, it will be considered a deviation and a deviation report

will be sent to the IRB within two weeks.

Table 1: Procedures

Procedures	Visit 1	Visit 2		Visit 3, 4, 5	Visit 6	
		Week 0		Weeks 2, 4, 6	Week 8	

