This visit will occur within four weeks from the Screening Visit. Participants will arrive on the NIA-Clinical Research Unit after a 12-hour fast. The following procedures will be done: vital signs, anthropometric measurements (weight, waist circumference, sagittal diameter), and a blood draw for clinical labs (CBC, PT, PTT, and INR to ensure safety of the LP), urine pregnancy test (only in women who are able to become pregnant), and research labs including DNA collection (for APOE genotyping and gene expression studies). A 4-hour mixed meal tolerance test will be done. They will also have cognitive testing and will be asked to complete the Symptoms Review Questionnaire, PANAS, and RAND SF-36. A lumbar puncture (LP) will take place; up to a total of 15 mL of CSF will be collected. Participants will have a brain MRI. About 168 mL of blood will be taken during the visit. To facilitate scheduling or satisfy a given participant's request, we may split the various procedures of the Baseline Visit over two days within a week from each other.

4.d.3. 5-2 CR or control groups

At the end of the Baseline Visit, all participants will receive informational materials and one-on-one dietary counseling about "healthy living", consisting of providing and reviewing published material (by the CDC and USDA) on meal portion control, calories in common beverages, meal substitutions for controlling calorie intake, and other dietary considerations. Participants will then be randomized by study investigators into one of two groups to either 1) implement 8 weeks of 5-2 CR (cases); or 2) implement "healthy living" diet (controls).

Participants in the 5-2 group will receive all shakes (Boost®, CWI Medical) from the NIA-Clinical Research Unit.

4.d.4. Compliance visits

To assess and reinforce compliance with their respective diet, we will contact participants by phone or email (via the Secure Email & File Transfer Service: <https://secureemail.nih.gov/bds/Login.do>) at weeks 1, 3, 5, 7 and four days after the Outcome Visit. In addition, we will conduct 2, 4, and 6 week Compliance Visits. The same procedure described below will occur during each one of these.

These visits will take place during the second of the two consecutive restriction days for the 5-2 CR group or any day for the "healthy living" diet group after an 8 hour fast. A blood draw to measure β-hydroxybutyrate, vital signs and anthropometric

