7.l. Brain MRI: The Food and Drug Administration (FDA) has recently established safety criteria for human exposure to MRI studies. The MRI scanner used in this study satisfies these safety criteria. People are at risk for injury from the MRI magnet if they have pacemakers or other implanted electrical devices, brain stimulators, dental implants, aneurysm clips (metal clips on the wall of a large artery), metallic prostheses (including metal pins and rods, heart valves, and cochlear implants), permanent eyeliner, implanted delivery pump, or shrapnel fragments. Welders and metal workers are also at risk for injury because of possible small metal fragments in the eye of which they may be unaware. Participants will be asked to complete an MRI screening form for each MRI. If any participant is found not to be eligible for the MRI or refuse the MRI, they will be disqualified from the study. In addition, all magnetic objects (for example, watches, coins, jewelry, and credit cards) will be removed before entering the MRI scan room. Participants with history of surgeries, implanted devices, etc. will be asked to provide us with surgical reports mentioning the type of the clips, prostheses, etc. used. Every effort will be made to establish the MR compatibility or incompatibility of these implants, according to the safety standards of the NIA 3T MRI center, including obtaining reports by manufacturing companies for MR compatibility. The research staff will evaluate each person with a less severe history of claustrophobia on a case-by-case basis.

Regarding minor discomforts, radiofrequency pulses emitted by the MRI machine can induce mild muscle twitching in some participants. If the sensation becomes overly uncomfortable, the scan will be stopped. The loud sounds (> 120 dB) emitted by the MRI machine during scanning require earplugs but may cause mild acoustic discomfort.

7.m. Cognitive Testing: Occasionally, cognitive tests may be tiring or stressful. Psychological testing may cause some people to feel anxious.

7.n. Genetic testing (APOE genotyping and DNA methylation studies): The DNA analysis that will be done as part of this study is done for research purposes only.

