The goal of this study is to provide proof of concept that 5-2 CR compared to dietary counseling can lower IR and ameliorate any detrimental effects on middle to older age cognitive performance, brain metabolism and function and normalize any biomarker abnormalities associated with higher risk of AD. Children do not develop AD, and there are no data to suggest that IR during childhood may impact future AD risk. In addition, 5-2 CR in juvenile animals permanently stunts their physical growth. Children are, therefore, not an appropriate population to examine for the purposes of our study.

11. c. Justification for exclusion of other vulnerable participants

If the present study provides proof of concept that 5-2 CR compared to dietary

counseling improves cognitive performance, brain metabolism and function and normalizes biomarker abnormalities associated with higher risk of AD, it would “pave the way” for testing it in cohorts with age-related cognitive impairment or AD. The study requires following strict instructions for 5-2 CR diet, which participants with cognitive impairment would find hard to follow. In addition, this is a proof of concept study that involves more than minimal risk without direct benefit. The study involves some minor but real discomfort (e.g. feeling hungry) and invasive procedures (such as LP), which are not appropriate for those without consent capacity in this study.

11. d. Justification of sensitive procedures

The experimental paradigm does not involve the use of deception, or other sensitive procedures.

11. e. Safeguards for vulnerable populations

We will perform pregnancy tests and exclude pregnant (and nursing) women.

11. f. Qualifications of investigators

The Principal Investigator has verified that all individuals working on this protocol required to take HRPP training under OHSRP SOP 25 (Training requirements for the NIH Human Research Protections Program) have completed all required training.

[name]. (LCI/NIA)

[name] is a Board-certified neurologist with subspecialty training on dementia and Experimental Therapeutics in Neurology. He will be principal investigator and medically responsible investigator of the protocol. He has been primarily responsible for the design of the study and will oversee the project, ensure quality assurance of the data and analyze the data. He will obtain consent, conduct History and Physicals and perform LPs.

[name]. (LNS/NIA)

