[name] is a Senior Research Fellow in the Laboratory of Neuroscience. She has completed her post-doctoral training in Neurosciences at University of California Los Angeles. She is also a licensed Nurse Practitioner and has practiced as a NP in the Johns Hopkins Neurology. [name] will be lead investigator on the protocol. She will be responsible for multiple clinical duties along with PI including overseeing participants' safety. She will obtain consent, conduct History and Physicals and perform LPs.

[name], MA, Ph.D. (LNS/NIA)

[name] is a Postdoctoral Fellow in the Human Neuroscience Unit under the training of [name]. He will be responsible for recruitment and contact with participants,

cognitive testing, MRI/fMRI/MRS, and data analysis. [name] has over 5 years of experience with neuropsych assessment and MRI research on patients with neurodegenerative diseases

12. Anticipated benefit

This pilot study of two short-term diets is not expected to generate direct benefits for the participant. While the diets are likely to decrease body weight and increase insulin sensitivity (i.e., decrease HOMA-IR), changes which may be desirable to the participants and their physicians, the changes are likely to be temporary. This is a short-term study and, therefore, the magnitude and duration of these effects and their impact on long-term health is unclear. The study will generate generalizable knowledge on the effects of short-term implementation of 5-2 CR.

13. Classification of Risk

13. a. For adults

Overall, we classify the study as greater than minimal risk.

13. b. For adults without consent capacity

Not applicable.

13. c. For children

Not applicable.

13. d. Overall risk and benefit consideration

The risks are reasonable in relation to anticipated benefit.

14. Consent Documents and Process

14. a. Designation of those obtaining consent

The principal investigator, clinical research coordinator (nurse) and NIA research nurses and nurse practitioners will be authorized to obtain consent. Investigators identified as being authorized to obtain consent in section 11.f. above will be allowed to obtain consent. In addition, NIA research nurses and nurse practitioners are qualified to obtain consent by their training and will also be authorized to obtain consent. All staff obtaining informed consent has completed the NIMH HSPU "Elements of Successful Informed Consent" training.

14. b. Consent procedures

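### Section 4.d.1 randomises before the Baseline Visit and section 4.d.3 at its end; under the 4.d.1 order, Baseline exclusions and baseline ratings would follow allocation

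*Combined protocol and SAP*

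**What the plan says.** Section 4.d.1, whose heading announces the chronological order of procedures, lists telephone pre-screening, the Screening Visit, "randomization into one of two groups", and only then the Baseline Visit.

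Section 4.d.3 gives a different order. "At the end of the Baseline Visit, all participants will receive informational materials" and one-on-one counselling. It continues: "Participants will then be randomized by study investigators into one of two groups".

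The Precis gives the ratio: participants "will be randomized 1:1 into 5-2 CR and control groups". Table 1 has no randomisation row. It does mark the review of inclusion and exclusion criteria at both Screening and Baseline.

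Some participants can leave at the Baseline Visit. On MRI, section 7.l says: "If any participant is found not to be eligible for the MRI or refuse the MRI, they will be disqualified from the study". The first study MRI is at Baseline. Section 7.h bars a participant with a positive pregnancy test, and that test is repeated at Baseline. Blood count and clotting tests are also repeated there before the lumbar puncture (4.d.2). Sections 3.a, 4.a and 10.b say that losses are replaced until 40 participants have complete data.

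Section 11.f describes the investigators' duties. Of the principal investigator it says: "He will obtain consent, conduct History and Physicals and perform LPs". The lead investigator has the same three duties. Of a third investigator it says: "He will be responsible for recruitment and contact with participants"; his duties also include cognitive testing, imaging and data analysis.

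**The concern.** Both statements are current operative text, so staff could follow either one. The order determines whether the Baseline Visit is truly pre-allocation.

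Two separate problems arise if allocation comes first. One is selection: a participant removed at Baseline has already been assigned, and whoever decides on removal, or the participant who refuses the scan, may know the arm. The other is measurement: ratings and performance tests labelled as baseline could be given by a tester, or answered by a participant, who knows the arm. A participant who knows the arm might also start to eat differently before the baseline blood draw and mixed meal test. Both problems affect the comparison with controls that the primary objective (section 2.a) relies on.

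**Working it through.** This is a comparison of passages. Arithmetic enters only in steps 1 and 4.

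1. **The plan's own figure.** Section 10.b states power above 90% for the primary outcome with 40 participants. Its inputs are f = 0.3, N = 40, m = 2 measurements and correlation 0.4. Under the G*Power default convention for a within-between interaction, the noncentrality is f² × N × m / (1 − 0.4) = 0.09 × 40 × 2 / 0.6 = 12.0, with 1 and 38 degrees of freedom. Power is about 92% at alpha 0.05 on the F test, or about 96% if the one-tailed test is run as alpha 0.10. The stated figure reproduces. No input depends on when randomisation happens, so correcting the order leaves it unchanged.

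2. **What falls before or after allocation.**

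| Step | 4.d.1 order | 4.d.3 order |
|---|---|---|
| Screening tests and eligibility | before | before |
| Accelerometry between Screening and Baseline | may be after | before |
| Eligibility re-review at Baseline (Table 1) | after | before |
| MRI ineligibility or refusal (7.l) | after | before |
| Repeat pregnancy and clotting tests | after | before |
| Cognition, PANAS, SF-36, symptom ratings | after | before |
| Baseline blood draw, mixed meal test, lumbar puncture, MRI | after | before |

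3. **Effect on the groups.** Under the 4.d.1 order, anyone removed at Baseline has been randomised. Enrolment continues until 40 have complete data, so the 40 analysed need not be the first 40 randomised. If removal depends on the arm, the two sets of completers are no longer comparable by design.

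4. **Can the model repair this?** Section 10.a fits Group, Time and their interaction at two time points. With complete data, the interaction estimates (mean change with 5-2 CR) − (mean change in controls). Suppose knowledge of the arm shifts the mean baseline by a in the 5-2 CR group and by b in controls, leaving the week-8 means alone. The estimate then moves by −(a − b). The model has no term that separates this from a diet effect. It also has no term for participants who were removed and contribute no data.

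5. **Which outcomes are exposed.** Tester or respondent knowledge matters most for cognition, PANAS, SF-36 and symptom ratings. The primary outcome is a laboratory ratio from plasma exosomes, which a tester is unlikely to influence. It could still be reached by early diet change, since the gap from Screening to Baseline is up to 3 weeks in 4.d.1 and up to 4 weeks in 4.d.2 and Table 2, and by selective removal.

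6. **Size.** The bias would need the number removed at Baseline by arm, or a value for a − b. The documents give neither, so no figure can be stated.

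**The case against.** The strongest reply is that the intended order is clear. Section 4.d.3 is the operative instruction, and 4.a.1 has the shakes tasted and supplied at the end of the Baseline Visit, which fits it. An optional Day 2 is described as part of the same visit, so the end of the visit naturally includes it. On this view the problem is one misplaced phrase in 4.d.1. Much of that stands: the baseline-measurement problem disappears under the 4.d.3 order. But 4.a.1 does not settle when assignment is made, Table 1 is silent, and nothing says that allocation waits for Day 2.

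Three stronger readings are tempting, and the documents do not support them.

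- **That 60 of 100 accruals leave room for arm-aware exclusion.** Sections 3.a and 10.b pool screening failures with withdrawals. Screening failures precede allocation under either order. Only removals at the Baseline Visit count here, and MRI and lumbar puncture contraindications are already on the telephone checklist (Attachment A). At ages 55 to 70, positive pregnancy tests should be rare.
- **That about 5 of 40 assignments are predictable.** Simple randomisation with each arm closed at 20 gives an expected forced run of 20 × C(40,20) / 2^39 = 5.0. The plan states neither simple randomisation nor such a cap. It counts completers, who are known only about 8 weeks after allocation.
- **That the people who recruit and test are the allocators.** Section 4.d.3 says only study investigators. The overlap is an inference from the duties in 11.f, and part of 11.f was missing from the text read for this point, so another investigator may hold that role.

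**Conclusion.** The contradiction between 4.d.1 and 4.d.3 is real and should be corrected. If 4.d.1 is followed as written, Baseline removals become post-randomisation exclusions and baseline ratings may be taken with the arm known. Participants could also change their diet before the baseline blood draw. The Group by Time analysis cannot undo these effects. The exposure is mainly in the rated and performance outcomes, which section 9 calls exploratory, and is smaller for the assay-based primary outcome. Its size and direction cannot be given.

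This rests on two assumptions: that some staff would follow 4.d.1, and that assignment under that order would be known before the Baseline procedures finish. The second is plausible because the available text describes no sequence generation, concealment or assessor blinding.

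Under the 4.d.3 order a smaller concern remains. If the next assignment is known or can be guessed by someone who also consents or recruits, entry could be influenced. The documents do not show that this would happen; they simply do not describe a safeguard.

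**What to change.** - Correct 4.d.1 to match 4.d.3. State that the assignment is revealed only after eligibility is confirmed and every baseline procedure, including any optional Day 2, is complete.
- Add a randomisation row to Table 1 at that point.
- State who generates the sequence, who holds it and how it is concealed. A pre-generated sequence released one participant at a time would do. It could be held by someone already on the study who does not recruit, test or run outcome assays, or kept in sealed opaque envelopes. The core laboratory is a doubtful holder because it stores the research samples. Random-sized blocks are one option among several.

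The cost is minor protocol wording and preparation of a list or envelopes. Sample size, alpha, power and the visit schedule do not change.
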